The present study aims to compare the acute and training responses of (1) eccentric high intensity interval training, (2) work-matched continuous eccentric training, and (3) concentric high intensity interval training, all performed on cycle ergometers. The variables of interest include ratings of perceived exertion (RPE), cognitive demand (Fat), heart rate (HR), maximal oxygen consumption ($VO_{2\text{max}}$), maximal aerobic power (MAP), and various functional and health-related parameters.

It is hypothesized that eccentric HIIT will produce comparable or superior improvements in functional outcomes relative to concentric HIIT, but at a lower metabolic and perceptual cost. Furthermore, eccentric HIIT is expected to yield greater physiological benefits than continuous eccentric training for a similar perceived and metabolic load.

II. Population

A. Recruitment

The study was conducted on sedentary individuals aged 50–75, engaging in no more than 3 hours of light-to-moderate activity per week.

Participants were recruited through:

- Notices in the Movement Sciences Department (ULiège, Blanc-Gravier),
- Social media,
- Professional/personal networks.

All participants are legal adults, volunteers, and signed an informed consent form, previously approved by the University Hospital Ethics Committee of Liège (ref 2023/072).

B. Sample Size Estimation

Given the study design (three groups, two time points), a repeated-measures ANOVA was selected to assess within-group changes, between-group differences, and potential group \times time interactions. The primary outcomes were changes in isometric maximal strength and maximal aerobic power. The significance level (α) was set at 2.5% to account for multiple primary comparisons.

Assuming a moderate to large effect size ($f = 0.3\text{--}0.5$) and a statistical power of 80%, the required total sample size was estimated to range from $n = 18$ to $n = 36$. Accounting for an anticipated dropout rate of 20%, the recommended sample size ranged from 8 to 15 participants per group. Sample size calculations were performed using *G*Power* software.

Inclusion criteria:

- Aged 55 to 75 yo;
- Sedentary or engaging in <3h of regular physical activity/week.

Exclusion criteria:

- Smoking;
- Recent lower limb injury or pain (past 6 months) interfering with ergocycle tests;
- Uncontrolled acute or chronic disease;
- Cardiovascular disorders.

III. Experimental Protocol

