Throughout each training session, HR was continuously monitored using a *Polar Verity Sense optical heart rate sensor* (*Polar Electro Oy, Finland*), worn on the upper arm and connected to the *Polar Flow* application via an *Apple iPad*. Both mean and maximal HR (mean HR and max HR) values were recorded per session. They are expressed in percentage of the maximal HR measured during the incremental cycling test (% max HR). For analysis, mean and max HR values were averaged for each of the three training phases.

2. Rating of Perceived Exertion

At the end of each training session, participants reported their RPE using the Borg RPE scale, ranging from 6 (no exertion) to 20 (maximal exertion). Average RPE values were calculated for each training phase and used for subsequent analysis.

3. Cognitive Demand

Perceived Fat was assessed following each session using a modified Borg scale ranging from 0 (no cognitive effort) to 10 (maximal cognitive effort). Participants were asked to evaluate the mental demand specifically related to the cognitive focus required during training. Phase-wise averages were computed for analysis.

4. Perceived Muscle Soreness

Prior to each training session, participants rated their perceived muscle soreness in the lower limbs using a visual analog scale (VAS) ranging from 0 millimeters (mm) (no soreness) to 200 mm (unbearable soreness). These ratings were intended to reflect residual soreness from the previous session. Means of each training phase were computed for statistical analysis.

E. Functional Parameters

A battery of six functional tests was performed pre- and post-intervention to evaluate intra-group improvements and inter-group differences. All tests were administered by the same trained evaluator to minimize inter-rater variability. Standardized instructions and verbal encouragement were provided to ensure consistency across participants.

1. Maximal Isometric Force (MIF)

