Aerobic endurance was evaluated via the 6MWT. Participants were instructed to walk as far as possible in six minutes along a 30-meter indoor track, turning around two cones at either end. HR and RPE were monitored throughout the test. The total distance covered was expressed in meters.

F. Statistical Analyses

All statistical analyses were conducted using R Commander (R version 4.4.2; R Foundation for Statistical Computing, Vienna, Austria). Data were initially assessed for normality using the Shapiro–Wilk test and for homogeneity of variances using Levene's test. For normally distributed variables with equal variances, repeated-measures analysis of variance (ANOVA) was used to examine the effects of time (pre- vs. post-intervention), group (EI, EC, CI), and their interaction. When significant main effects or interactions were found, post hoc comparisons were performed using Tukey's Honestly Significant Difference (HSD) test to control for Type I error.

For outcome variables related to participants characteristics and functional performance that did not meet the assumptions of normality, non-parametric tests were applied. Specifically, within-group comparisons across time were conducted using the Wilcoxon signed-rank test, and between-group comparisons were evaluated using the Kruskal–Wallis test.

All results were considered statistically significant at $p < 0.05$. Data are presented as mean \pm standard deviation (SD) for parametric variables and as median with interquartile range (IQR) for non-parametric variables, unless otherwise stated.

Summary

Phase 0 – Testing	Week –1 (2 sessions)	Evaluation
Phase 1 – Familiarization	Week 2-3 (2x/wk)	5' 20% MAP - 10' 30% MAP 15' 30% MAP - 20' 40% MAP 5' 20% - 10' 20% 15' 30% - 20' 30%
	Week 4-5 (EC, 2x/wk)	20' 40 et 50 % MAP, 60 rpm 30' 50 et 60% MAP, 60 rpm
	Week 4-5 (EI, 2x/wk)	6 x 2'-1' à 60 et 80% MAP, 60 rpm 9 x 2'-1' à 80 et 100% MAP, 60 rpm
	Week 4-5 (CI, 2x/wk)	6 x 2'-1' à 40 et 50% MAP, 60 rpm 9 x 2'-1' à 50 et 65% MAP, 60 rpm
Phase 2 – Training	Week 6-9 (EC, 3x/wk)	30' 80% MAP, 60 rpm
	Week 6-9 (EI, 3x/wk)	10 x 2'-1' 120% MAP, 60 rpm
	Week 6-9 (CI, 3x/wk)	10 x 2'-1' 80% MAP, 60 rpm
Phase 3 – Training	Week 10 – 13 (EC, 3x/wk)	30' 90% MAP, 60 rpm
	Week 10 – 13 (EI, 3x/wk)	10 x 2'-1' 135% MAP, 60 rpm
	Week 10 – 13 (CI, 3x/wk)	10 x 2'-1' 90% MAP, 60 rpm
Phase 4 – Retesting	Week 14	Evaluation

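### Pre/post outcomes: the plan should tie between-arm claims to the group × time interaction it already includes, and say that Kruskal–Wallis is run on change

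*Combined protocol and SAP*

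**What the plan says.** For outcomes that meet the normality and variance checks, section III.F says that a repeated-measures ANOVA "was used to examine the effects of time (pre- vs. post-intervention), group (EI, EC, CI), and their interaction". The three effects have equal standing. The post hoc rule follows: "When significant main effects or interactions were found, post hoc comparisons were performed using" Tukey's HSD.

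The non-parametric branch is introduced by "For outcome variables related to participants characteristics and functional performance that did not meet the assumptions of normality". Within arms it uses the Wilcoxon signed-rank test; for the rest, "between-group comparisons were evaluated using the Kruskal–Wallis test". The response for that test (pre, post or change) is not given, and no pairwise follow-up is named.

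Other sections bear on the intent. In section II.B, "The primary outcomes were changes in isometric maximal strength and maximal aerobic power". The same section says the ANOVA was chosen "to assess within-group changes, between-group differences, and potential group" × time interactions, so between-group differences are listed apart from the interaction. The hypothesis in section I is that "eccentric HIIT will produce comparable or superior improvements in functional outcomes relative to concentric HIIT". Section III.E says the six functional tests, which include the primary strength outcome, serve "to evaluate intra-group improvements and inter-group differences".

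**The concern.** The trial asks whether eccentric interval training (EI) improves outcomes differently from concentric interval (CI) and eccentric continuous (EC) training. With one pre and one post value per participant, that is the group × time interaction, or equivalently a comparison of change between arms.

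The group main effect answers another question. It compares the average of the pre and post values, so it halves a difference that appears only after training and adds in any chance difference at baseline. Arms of 8 to 15 leave room for such differences. Since the post hoc rule treats both effects alike, and the text never says which one supports a between-arm claim, two routes to such a claim are open for each outcome. A significant time effect does no harm here, because it concerns only two time points and says nothing about the arms.

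For non-normal pre/post outcomes the gap is different: no test of differential change is committed to. Wilcoxon looks within one arm at a time, and Kruskal–Wallis could be run on post values or on change. Those choices can differ widely in power.

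**Working it through.** **Inputs.** From section II.B: three groups, two time points, alpha 0.025, power 80%, f = 0.3 to 0.5, total N = 18 to 36, 20% dropout, 8 to 15 per group. From section III.F: significance at 0.05. The pre/post correlation ρ is not stated; 0.5 is assumed first and a range is shown. Equal allocation is assumed.

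**1. Which effect does the stated N fit?** Noncentral F, N in multiples of 3.
- Interaction: λ = 2f²N/(1−ρ), df 2 and N−3. For f = 0.3, N = 36: λ = 2(0.09)(36)/0.5 = 12.96, power 0.803 (N = 33 gives 0.756). For f = 0.5, N = 18: λ = 2(0.25)(18)/0.5 = 18, power 0.879 (N = 15 gives 0.773). Required N is therefore 18 to 36, as stated.
- Dropout: 18/0.8 = 22.5 and 36/0.8 = 45, giving 8 and 15 per group, as stated.
- Time effect (same λ, df 1 and N−3): required N is 15 to 30, no match.
- Group main effect, λ = 2f²N/(1+ρ): required N is 39 to 102, no match.

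Across ρ = 0.3 to 0.8 the interaction N runs from 21–51 down to 12–18, so the match depends on ρ = 0.5.

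**2. Power of the group main effect at the planned N.** A training difference seen only at post gives the same f for both effects, so λ shrinks by (1−ρ)/(1+ρ), which is one third at ρ = 0.5. λ = 4.32 (N = 36, f = 0.3) gives power 0.299; λ = 6 (N = 18, f = 0.5) gives 0.367.

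**3. False signals if either effect were read as a training difference.** With equal variances at both times, the sum and the difference of pre and post are uncorrelated, so the two tests are nearly independent: 1 − 0.95² = 9.75%, and at alpha 0.025, 1 − 0.975² = 4.94%. Simulation at 0.05 (100,000 trials per cell, 6 to 15 per arm, ρ 0.5 and 0.8, equal gain in all arms) agrees:

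| Rule | Rate with no arm difference |
|---|---|
| Interaction only | 4.9–5.1% |
| Interaction or group effect | 9.6–9.9% |
| Same, and matching Tukey test significant | 8.8–9.0% |
| Tukey on change | 4.9–5.1% |

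**4. Kruskal–Wallis on post or on change.** A post value has variance σ² and change has 2σ²(1−ρ); these are equal at ρ = 0.5. Simulated power at 0.05, N = 18 to 36, one arm better, effect set so that the interaction test has 0.80 power:

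| ρ | Normal: post | Normal: change | Skewed: post | Skewed: change |
|---|---|---|---|---|
| 0.3 | 0.88–0.90 | 0.74–0.77 | – | – |
| 0.5 | 0.74–0.77 | 0.74–0.77 | 0.83–0.90 | 0.79–0.87 |
| 0.7 | 0.51–0.53 | 0.74–0.77 | 0.64–0.72 | 0.79–0.87 |
| 0.8 | 0.35–0.38 | 0.74–0.77 | 0.49–0.55 | 0.79–0.87 |

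The skewed model is an assumption (shared and visit-specific lognormal parts, log-SD 0.6). The crossover lies near ρ = 0.5 for normal data and 0.55 for this skewed model. With no arm difference, change alone gives 4.2–4.8%; trying both and keeping either gives 8.0–9.1%.

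**5. Baseline adjustment.** ANCOVA of post on group and baseline, alpha 0.025, N = 18 to 36, interaction power held at 0.80: 0.88–0.90 at ρ = 0.5, 0.83–0.86 at 0.7, 0.81–0.83 at 0.8, 0.79–0.81 at 0.9.

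**The case against.** The strongest reply is that the right test is already there. Section II.B makes changes primary, section I speaks of improvements, section III.F includes the interaction, and the sample size fits it. The post hoc sentence is ordinary ANOVA wording, and opening Tukey tests after a group effect is not the same as claiming a training effect. This largely stands, and it keeps the point minor. What it does not do is close the second route or settle the Kruskal–Wallis response. The intent behind the sample size also shows only by back-calculation with an assumed correlation.

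A reader might go further and infer that the plan has no valid between-arm test, or that its error rate is 10%. The documents support neither. The interaction is planned and valid. The 10% figure needs the group effect to be read as a training difference, which is not stated, and it needs the 0.05 level of section III.F; at section II.B's 2.5% it is about 5%.

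Nor is Kruskal–Wallis on post values wrong. In a randomised trial it holds its level (4 to 5% in simulation), and at low correlation it is the more powerful choice. The branch is also meant for non-normal data, so the skewed columns are the more relevant ones, and there the loss is smaller. Finally, the branch covers functional performance and participant characteristics. Section III.A lists the incremental test apart from the six functional tests, so maximal aerobic power may fall outside it; isometric strength falls inside.

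**Conclusion.** The point holds as a minor, cheap improvement. For pre/post outcomes the plan contains the correct between-arm test but does not bind its between-arm claims to it. The alternative that the post hoc rule admits is weak (power 0.30 to 0.37 at the planned N) and, if used alongside the interaction, would roughly double the false-signal rate per outcome. For non-normal pre/post outcomes no test of differential change is fixed; at ρ = 0.8 the unstated choice moves power from 0.74–0.77 to 0.35–0.38 with normal data, or from 0.79–0.87 to 0.49–0.55 with the skewed model.

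These sizes rest on assumed correlations, equal arms and, for the skewed results, an assumed distribution. Participant characteristics and the phase-averaged heart rate, RPE, cognitive demand and soreness measures are not affected; for the phase-averaged measures a group main effect can be a proper question. The difference between the 2.5% and 5% levels is a separate matter.

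**What to change.** For pre/post outcomes only:

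1. State that between-arm claims rest on the group × time interaction. Run the between-arm Tukey contrasts (EI–CI, EI–EC, EC–CI) on change, post minus pre, and only after a significant interaction. State that the group main effect is not interpreted as a training effect.
2. Where the non-parametric branch applies, run Kruskal–Wallis on change, followed by multiplicity-adjusted pairwise rank tests on change.
3. Report an ANCOVA of the post value on group and baseline. Make it the main test only if outcome data have not been seen. Otherwise keep the interaction as the main test and report ANCOVA as a sensitivity analysis; section III.F is written in the past tense, so the sponsor should say which case applies.

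Cost: steps 1 and 2 are wording plus one set of rank tests, with no new data or participants, and the sample size for the interaction stays at 18 to 36. Kruskal–Wallis on change gives up some power if ρ is below about 0.5 to 0.55 (normal data at ρ = 0.3: 0.74–0.77 against 0.88–0.90 on post values). ANCOVA is one model line and one residual degree of freedom. It gains little above ρ of about 0.8, and at N = 18 is level with or slightly below the interaction from about 0.83 to 0.85.

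### At the plan's lower size (6 analysed per arm), the fallback per-arm Wilcoxon test for isometric strength cannot reach the 2.5% level set in II.B if that level governs and the test is two-sided

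*Combined protocol and SAP*

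**What the plan says.** Section II.B (Sample Size Estimation) defines the primary endpoints: "The primary outcomes were changes in isometric maximal strength and maximal aerobic power". On the level it says: "The significance level (α) was set at 2.5% to account for multiple primary comparisons". With f between 0.3 and 0.5 and 80% power it requires 18 to 36 participants in total. After allowing for 20% dropout, "the recommended sample size ranged from 8 to 15 participants per group".

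Section III.F (Statistical Analyses) uses repeated-measures ANOVA when the normality and variance checks pass. For participant characteristics and functional-performance variables that fail normality, "within-group comparisons across time were conducted using the Wilcoxon signed-rank test", and groups are compared by Kruskal–Wallis. It then says "All results were considered statistically significant at" p < 0.05, with no separate level for the primary outcomes. It does not say whether tests are one- or two-sided.

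Maximal isometric force is the first of the six tests in III.E (Functional Parameters), so the fallback covers it. Maximal aerobic power is not in that battery, so this point is confined to strength.

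**The concern.** An exact signed-rank test on a handful of pairs can take only a few p-values, and the smallest of them may lie above the chosen level. If it does, the test cannot reject even when every participant in the arm improves.

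That matters here because within-group change is a declared aim, both in II.B and in the introduction to III.E. Once the fallback is triggered, the per-arm Wilcoxon test is also the only test of time in the plan. Arms may finish with different numbers, too. The same pattern, everyone improving, could then be significant in an arm of 7 and not in an arm of 6, and a reader could mistake that for a difference between training modes.

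**Working it through.** **Inputs.** From II.B: 3 groups, 2 time points, level 0.025, power 80%, f = 0.3 to 0.5, dropout 20%. From III.F: per-arm signed-rank test, level 0.05, R 4.4.2. Assumed because not stated: equal allocation, two-sided tests, pre–post correlation 0.5 with sphericity, and dropout independent between participants.

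**1. The plan's own sizes.** For the group-by-time interaction, the noncentrality is λ = f²·N·m/(1 − ρ) = 4f²N with m = 2 and ρ = 0.5, on 2 and N − 3 degrees of freedom, at level 0.025:
- f = 0.5: N = 15 gives power 0.773; N = 18 gives 0.879.
- f = 0.3: N = 33 gives power 0.756; N = 36 gives 0.803.

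This reproduces 18 and 36. At level 0.05 with the same correlation, the sizes would be 15 and 30, so the stated sizes fit 2.5%.

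Dropout: 18/3 = 6 and 6/0.8 = 7.5, rounded up to 8; 36/3 = 12 and 12/0.8 = 15. Both match the plan.

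**2. Floor of the per-arm test.** With n non-zero, untied changes there are 2ⁿ equally likely sign patterns under the null, so the smallest exact two-sided p is 2/2ⁿ.

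| Analysed in arm | Smallest two-sided p | 2.5% reachable | 5% reachable |
|---|---|---|---|
| 5 | 2/32 = 0.0625 | no | no |
| 6 | 2/64 = 0.03125 | no | yes |
| 7 | 2/128 = 0.0156 | yes | yes |
| 8 | 2/256 = 0.0078 | yes | yes |
| 12 | 2/4096 = 0.0005 | yes | yes |

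At n = 6 the next exact value is 4/64 = 0.0625, so 5% is met only if all six changes have the same sign. As an illustration, if each participant had an 80% chance of improving, all six would improve with probability 0.8⁶ = 0.26. A zero change drops out of the ranking, leaving 5 pairs and an exact floor of 0.0625.

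**3. Ties.** With ties, R's default changes to a normal approximation with continuity correction. At n = 6, with all changes in one direction, six identical changes give p = 0.0197. Every other tie pattern gives at least 0.0263. At n = 5, p falls below 0.05 only when at least four changes tie (0.0477 for four, 0.0369 for five).

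**4. How often an arm is this small.** With 8 recruited and each retained with probability 0.8:
- P(8) = 0.168 and P(7) = 0.336, so P(6 or fewer) = 1 − 0.503 = 0.497.
- At least one of three arms with 6 or fewer: 1 − 0.503³ = 0.87.
- P(5 or fewer) = 0.20; at least one of three arms: 0.49.

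With 12 recruited per arm, P(6 or fewer) is about 2%. With 15 it is about 0.1%.

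**The case against.** The strongest reply is that III.F, where the test is specified, sets 5% for all results, and six pairs can reach 5%. That is correct, and it is why the conclusion is conditional on the level. It does not dispose of the point. II.B adopted 2.5% because there are two primary outcomes, the sample sizes fit that level, and using 5% for both gives up the stated multiplicity control. Even at 5%, six pairs need a unanimous direction.

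Second, sidedness is not stated. A one-sided test at n = 6 could reach 1/64 = 0.0156. This stands as a limit, although nothing in the plan specifies a one-sided test.

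Third, the trial's hypotheses compare training modes, and the between-group test under the fallback is Kruskal–Wallis, which has no comparable floor: 18 people can be split into three arms of 6 in 17,153,136 ways. This also stands. The limitation concerns change within an arm, which is a declared aim but is not shown to be the deciding test.

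Fourth, the plan gives a range and does not fix 18. With 8 recruited, a given arm keeps 7 or 8 people about half the time, and at the upper size the problem is negligible.

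A reader might infer that the strength analysis must fail whatever the data, or that sample size, level and fallback are incompatible throughout. The documents do not support that. The floor binds only in an arm with 6 or fewer analysed, after failed normality, for a two-sided test at 2.5%, and it has the tied exception shown above.

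**Conclusion.** The point holds as a conditional defect in the choice of fallback test. No figure in the plan is miscalculated; 18, 36, 8 and 15 all reproduce.

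Two things follow. First, II.B and III.F state different significance levels for the primary outcomes and must be reconciled. Second, if 2.5% governs and tests are two-sided, the per-arm signed-rank test for strength cannot be significant in an arm with 6 analysed (0.031 against 0.025), apart from the implausible case of six identical changes. If 5% governs, 6 analysed suffice only with a unanimous direction on the exact test. With 5 analysed the exact test cannot reach 5%, and only heavy ties under R's approximation would change that.

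The exposure is real at the lower recruitment figure: about an even chance for any one arm and 0.87 for at least one of three, under independent 20% dropout. It vanishes with 7 or more analysed per arm. The ANOVA is untouched, and so is the Kruskal–Wallis comparison.

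**What to change.** In III.F:
- State that the 2.5% level applies to the two primary outcomes, and state the sidedness of the tests.
- For strength under the fallback, do not use separate per-arm Wilcoxon tests as decision tests.
- Test the group difference by Kruskal–Wallis, or by a permutation test of arm labels, on the pre–post changes of all randomised arms.
- Test the overall time effect by one signed-rank or sign-flip test over all 18 to 36 participants. At 18 the floor is 2/2¹⁸ = 0.000008. This test is needed separately, because permuting arm labels addresses only differences between arms.
- Report within-arm changes as estimates with intervals. If these are signed-rank intervals, give the achieved coverage: with 6 pairs it cannot exceed 1 − 0.03125 = 96.9%.

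In II.B, add that 6 per arm does not support a two-sided per-arm signed-rank test at 2.5%.

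The cost is a few sentences and no extra participants. The downside is that there are no per-arm p-values for strength under the fallback.

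### The sample size section sets alpha at 2.5% for the primary comparisons, but the analysis section calls every result significant at p < 0.05, so a primary p-value between the two has no settled verdict.

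*Combined protocol and SAP*

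**What the plan says.** Section II.B (Sample Size Estimation) defines the primary outcomes: "The primary outcomes were changes in isometric maximal strength and maximal aerobic power". It then says "The significance level (α) was set at 2.5% to account for multiple primary comparisons". The same section selects a repeated-measures ANOVA for three groups and two time points. It gives a total of 18 to 36 participants for f = 0.5 down to 0.3 at 80% power, or 8 to 15 per group after 20% dropout.

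Section III.F (Statistical Analyses) says the ANOVA "was used to examine the effects of time (pre- vs. post-intervention), group (EI, EC, CI), and their interaction". After a significant effect it uses Tukey's "Honestly Significant Difference (HSD) test to control for Type I error". It also provides an alternative route: "For outcome variables related to participants characteristics and functional performance that did not meet the assumptions of normality, non-parametric tests were applied". On that route, change within each group is tested by Wilcoxon signed-rank and groups are compared by Kruskal–Wallis. The section closes with "All results were considered statistically significant at $p < 0.05". It does not mention 2.5%, adjusted p-values or different treatment of the primary outcomes.

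Maximal isometric force is the first test in the III.E battery, described thus: "A battery of six functional tests was performed pre- and post-intervention to evaluate intra-group improvements and inter-group differences". One of the two primary outcomes can therefore be sent to the non-parametric route.

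**The concern.** A reduced alpha chosen for multiplicity protects against false positives only if it is also the level used for testing. Here the reduced level stands in the sample size section and the full 5% in the only decision rule. The most natural reading of 2.5% is 5% split equally over the two primary outcomes. III.F removes that split.

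This is the decision rule for the trial's main conclusions. With both thresholds in the text, a primary p-value between 0.025 and 0.05 can be reported either way, and the choice could be made after the p-value is known.

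Two further gaps mean that changing one number is not enough. III.F lists three ANOVA effects without saying which is the primary test. It also attaches no level other than 0.05 to the non-parametric route that maximal isometric force may take.

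**Working it through.** **1. The two rules side by side.** II.B: alpha 0.025, given as a multiplicity adjustment. III.F: 0.05 for all results. For p = 0.03 on a primary outcome, 0.03 > 0.025 is negative and 0.03 < 0.05 is positive.

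**2. The plan's own sample size.** Inputs from II.B: k = 3 groups, m = 2 time points, alpha = 0.025, power 80%, f = 0.3 and 0.5. The pre-post correlation rho is not given; 0.5 is assumed. For the group-by-time interaction:

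- lambda = f² × N × m / (1 − rho), df1 = (k − 1)(m − 1) = 2, df2 = (N − k)(m − 1) = N − 3.
- f = 0.3, N = 36: lambda = 0.09 × 36 × 2 / 0.5 = 12.96, critical F(2, 33) = 4.13, power 0.803.
- f = 0.5, N = 18: lambda = 0.25 × 18 × 2 / 0.5 = 18, critical F(2, 15) = 4.77, power 0.879.
- In multiples of 3, these are the smallest N reaching 80%, so 36 and 18 are reproduced.
- Dropout: 36 / 0.8 = 45, or 15 per group; 18 / 0.8 = 22.5, rounded up to 23, or 8 per group. Both match.

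At alpha 0.05 with rho = 0.5 the same formula gives 30 and 15. However, alpha 0.05 with rho of 0.39 to 0.40 also gives 36 and 18. The stated N therefore agrees with 2.5% but does not prove which alpha was used. The 2.5% rests on the sentence in II.B.

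**3. Family-wise error over the two primary outcomes.** One group-by-time test per outcome. With two time points this equals a one-way F test on change scores.

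- Upper bound, whatever the correlation: 2 × 0.05 = 0.10; 2 × 0.025 = 0.05.
- Independent outcomes: 1 − 0.95² = 0.0975; 1 − 0.975² = 0.0494.
- Correlated outcomes, by simulation under no effect (3 groups of 12, 1.2 million runs per correlation). The documents give no between-outcome correlation, so the range is an assumption:

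| Correlation between outcomes | 0.05 each | 0.025 each | Tukey pair declared after a significant F, 0.05 | Same, 0.025 |
|---|---|---|---|---|
| 0 | 9.75% | 4.9% | 8.8% | 4.4% |
| 0.5 | 9.2% | 4.7% | 8.4% | 4.2% |
| 0.7 | 8.5% | 4.4% | 7.7% | 3.9% |

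Requiring a significant Tukey pair lowers the error only slightly, because Tukey adjusts across group pairs within an outcome and not across outcomes.

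**4. Why one test must be named.** If time, group and interaction all counted for both outcomes (six tests, independence and no true effect assumed), the error would be 1 − 0.95⁶ = 26.5% at 0.05 and 1 − 0.975⁶ = 14.1% at 0.025.

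**5. How often the disputed zone is hit.** With rho = 0.5, the chance that a primary p-value falls between 0.025 and 0.05 is the difference in power. It is 0.878 − 0.803 = 7.5% at f = 0.3, N = 36, and 0.938 − 0.879 = 5.9% at f = 0.5, N = 18. With no true effect it is 2.5%.

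**The case against.** The strongest defence is that the 2.5% appears only in the sample size section, so III.F is the sole decision rule and 2.5% was conservative planning. II.B does not support this, because it gives multiplicity as the reason, and that purpose is served only at the testing stage.

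A second defence is that the comparisons meant are the two hypothesised contrasts, eccentric interval against concentric interval and against eccentric continuous, which Tukey covers. That reading is possible. Even so, 2.5% is absent from III.F and nothing adjusts across the two outcomes.

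Several limits on the argument do stand:

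- The six-test figures assume no time effect in any arm, although all arms train and improvement is expected. The plan also does not say that any one effect counts as success. They show why a primary test must be named, and should not be read as the trial's error rate.
- Power at 0.025 depends on rho. At f = 0.3 and N = 36 it is 0.63, 0.71, 0.80 and 0.97 for rho 0.3, 0.4, 0.5 and 0.7. Reaching 80% at f = 0.3 needs 51 participants at rho 0.3 and 45 at rho 0.4. At N = 18 and f = 0.3 (rho 0.5) power is 0.40.
- III.F states no pairwise tests after Kruskal–Wallis. What it lists without adjustment is one Wilcoxon test per group.
- Holm's procedure at an overall 5% would also settle the conflict.

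None of these removes the contradiction between the two sections.

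**Conclusion.** The concern holds and must be fixed. Both thresholds are in the current text, nothing reconciles them, and the stated decision rule undoes the stated multiplicity control. The contradiction itself needs no assumption. Its size, for one group-by-time test per primary outcome, is a family-wise error of at most 10% where II.B implies at most 5%, so roughly double. The bounds hold for any correlation between the outcomes; the figures below them depend on the assumed correlation. Reading 2.5% as 5% divided over two outcomes is the most natural interpretation, but II.B does not say so outright.

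**What to change.** In III.F, replace the single threshold with wording such as:

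*For each of the two primary outcomes (maximal isometric force and MAP), the one primary test is the group-by-time interaction, equivalently the between-group comparison of pre-to-post change, tested at p < 0.025. Tukey comparisons of change within a primary outcome follow only if that test is significant, at a family-wise level of 0.025. If a primary outcome fails the normality assumption, Kruskal–Wallis is applied to its change scores at the same 0.025 level, with multiplicity-adjusted pairwise comparisons. All other tests use a nominal 0.05.*

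Also state the route for a primary outcome that is normal but has unequal variances, since III.F limits ANOVA to equal variances and offers the alternative only for non-normality. In II.B, add what the 2.5% is divided over and the pre-post correlation used. Holm at an overall 5% is an acceptable substitute if named in advance. If results have already been seen, apply the 2.5% given in II.B and disclose the inconsistency.

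The cost is a few sentences in III.F, a clause or two in II.B and a stricter threshold for two outcomes. With rho = 0.5, moving from 0.05 to 0.025 lowers power from 0.88 to 0.80 (f = 0.3, N = 36) and from 0.94 to 0.88 (f = 0.5, N = 18), so no participants are added. If the sponsor's rho is below about 0.5, N for f = 0.3 needs rechecking.
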